2.4.3.2 Compliance

A given administration will be considered noncompliant if the patient did not take the planned dose of treatment as required by the protocol. No imputation will be made for patients with missing or incomplete data.

Percentage of compliance for a participant will be defined as (number of study drug administrations received / number of study drug administration planned)*100 (%).

Treatment compliance will be summarized descriptively by analysis period and analysis subperiod as quantitative variables (number, mean, SD, median, minimum, and maximum) for the recurrence population.

Cases of overdose (see protocol for further details) will constitute AEs and will be listed as such.

2.4.4 Analyses of efficacy endpoints

All efficacy endpoints related to assessments on the Q6M FU visits will be analyzed using the ITO population. Summarization will be conducted on the total study population and by analysis group. For the group-wise analysis, the following groups will be considered:

- caplacizumab-treated: defined as subjects in the ITO population who have been randomized to caplacizumab in study ALX0681-C301, evaluated up to their first recurrence in the ALX0681-C302 trial;
- standard of care-treated, defined as subjects in the ITO population who have been randomized to placebo in study ALX0681-C301, evaluated up to their first recurrence in the ALX0681-C302 trial.

Subjects who had a recurrence during study ALX0681-C301 or between the Final (28 day) FU visit in study ALX0681-C301 and Screening/Baseline in study ALX0681-C302, will not be considered for the group-wise analyses.

All efficacy endpoints related to assessments during the recurrence period will be analyzed using the recurrence population. The effect of retreatment of caplacizumab on these endpoints will be evaluated. For the group-wise analysis the following groups are considered, unless otherwise specified:

- Treated with IMP: defined as subjects in the recurrence population who received caplacizumab in the ALX0681-C302 during a recurrence episode
- Not treated with IMP: defined as subjects in the recurrence population who did not receive caplacizumab in the ALX0681-C302 during a recurrence episode.

Of note, depending on the recurrence episode, the same subject can appear in both analysis groups.

Select sensitivity analyses may be planned to assess the effect of heterogeneity in the timings of the baseline visit between subjects. Unless specified otherwise, no missing data imputation will be applied, and all efficacy endpoints will be analyzed as observed.

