[figure not shown]
collected as will safety information (including AEs, safety laboratory parameters, vital signs and physical examination), and determination of PK, ADA, PD parameters (vWF:Ag and RICO), and disease-related markers (ADAMTS13 activity and TnI).

In case of recurrent thrombocytopenia requiring re-initiation of daily PE during an ongoing recurrence period (see [Figure 4](#) and [Table 2](#)), a new visit cycle is to be started, with a recurrence visit on the day of the new recurrence followed by all subsequent visits as indicated in [Table 2](#). All remaining visits of the original schedule are no longer applicable and are not to be performed.

Note: an i.v. loading dose of caplacizumab needs to be administered prior to re-initiation of PE for the recurrence.

Q6M visits that are scheduled within a recurrence period will not be held as assessments at such visits would be confounded by the concurrent recurrence.

Note: Treatment with caplacizumab may not be initiated for subjects who do not fulfil the caplacizumab treatment criteria (see section [3.2.3](#)). Hence, these subjects will be treated with standard of care only. The visit schedule in case of initiation of only standard of care treatment includes a recurrence visit at presentation and a recurrence FU visit at 30 days after end of daily PE (see [Appendix 1](#) for schedule of assessments).

M: month; Y: year

Figure 4: Study flow of Study ALX0681-C302.

Treatment in case of recurrence:

Standard of care treatment (per standard site practice) can include:

- PE with plasma (e.g., fresh frozen plasma, solvent detergent/viral-inactivated plasma, cryosupernatant)
- Corticosteroid treatment
- Use of other immunosuppressive agents (e.g., rituximab)

Initiation of treatment with caplacizumab^{§§}:

Daily PE period

- Loading i.v. dose: subjects will receive a single loading dose of 10 mg study drug by i.v. bolus injection from 6 hours to 15 minutes prior to start of daily PE treatment^{***}.
- Daily s.c. dose: within 2 hours after completing each daily PE, a s.c. injection of 10 mg study drug will be administered daily throughout the full duration of PE treatment.

30-day post-daily PE period

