3.4.1.2. ASSESSMENT PERIOD (Q6M VISITS)

Subjects will be asked to attend Q6M visits for 3 years starting from a screening/baseline visit.

Assessments at the Q6M visits will include (also see [Schedules of Assessments](#)):

- Concomitant medication
- Adverse events
- Physical examination, vital signs
- Clinical laboratory analyses include chemistry (aspartate aminotransferase [AST], alanine aminotransferase [ALT], LDH, creatinine, protein, C-reactive protein [CRP], cholesterol) and hematology (hemoglobin [Hb], hematocrit [Hct], red blood cells [RBC], white blood cells [WBC], platelets). Urinalysis includes assessment of albumin.
- Cognitive assessment: Repeatable Battery for the Assessment of Neuropsychological Status (RBANS) (only at screening/baseline and the 36-month visit and only in those countries where RBANS is available in the local language[s])
- Quality of life assessment: SF36 questionnaire
- Headache Impact Test (HIT-6™)
- Organ damage marker: troponin (TnI)
- ADAMTS13 activity

- PD parameter: vWF:Ag
- Immunogenicity: ADA panel

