(1) caplacizumab-treated, defined as subjects in the ITO population who have been randomized to caplacizumab in Study ALX0681-C301, evaluated up to their first recurrence⁺⁺⁺; (2) standard of care-treated, defined as subjects in the ITO population who have been randomized to placebo in Study ALX0681-C301, evaluated up to their first recurrence.

All efficacy endpoints related to assessments during the recurrence period will be analyzed using the recurrence population. The effect of retreatment of caplacizumab on these endpoints will be evaluated.

Select sensitivity analyses may be planned to assess the effect of heterogeneity in the timings of the baseline visit between subjects. More details will be provided in the SAP. Unless specified otherwise, no missing data imputation will be applied, and all efficacy endpoints will be analyzed as observed.

3.6.5. EVALUATION OF PHARMACOKINETIC AND PHARMACODYNAMIC, DISEASE RELATED MARKERS AND IMMUNOGENICITY PARAMETERS

Individual study drug concentrations will be listed. In addition a listing of the actual sampling times relative to the study drug administration times will be presented.

Drug concentrations will be summarized by sampling time using descriptive statistics and will be listed and summarized in tabular and/or graphical form.

All PD and disease-related marker data will be summarized using descriptive statistics and will be listed and summarized in tabular and/or graphical form.

Immunogenicity will be assessed through listing of individual (ADA, mADA and nAb) results by subject, summary tables and immunogenicity time profiles. Immunogenicity data will be correlated with PK and PD readout using descriptive statistics per subject category based on pre-Ab and TE ADA status (using ADA results obtained in Study ALX0681-C301), summarized in tabular and/or graphical form. In addition, immunogenicity will be correlated with possible safety findings. The effect of retreatment with caplacizumab on immunogenicity will be assessed.

⁺⁺⁺ Subjects who had a recurrence during Study ALX0681-C301 or between the Final (28 day) FU visit in Study ALX0681-C301 and Screening/Baseline in Study ALX0681-C302, will not be considered for the group-wise analyses.

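### By-arm follow-up stops at first recurrence while RBANS has a single post-baseline assessment, so the by-arm cognitive change comes only from subjects without a recurrence

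*SAP*

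**What the plan says.** SAP 2.4.4 sets the scope: "All efficacy endpoints related to assessments on the Q6M FU visits will be analyzed using the ITO population". It then states that "Summarization will be conducted on the total study population and by analysis group". The two analysis groups are the subjects randomised to caplacizumab and to placebo in C301, each "evaluated up to their first recurrence in the ALX0681-C302 trial". Protocol 3.6.4 has the same rule; its second group is defined as those "randomized to placebo in Study ALX0681-C301, evaluated up to their first recurrence". Subjects who recurred in C301, or between the end of C301 and the C302 baseline, "will not be considered for the group-wise analyses". No cut-off is stated for the total-population summary.

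Protocol 3.4.1.2 schedules RBANS "only at screening/baseline and the 36-month visit", and only where a local-language version exists. In the visit schedules (protocol Table 1, SAP Table 4) the 36-month column is shared with the early termination visit. SAP 2.4.4.6 summarises the RBANS score and its change from baseline for the ITO population and compares the score descriptively with the reference population.

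The protocol synopsis lists cognitive function, mortality and number of recurrences among the main endpoints.

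**The concern.** Each rule is reasonable alone; the difficulty is their combination. An endpoint measured every six months loses only its later visits when follow-up stops at recurrence. An endpoint with one post-baseline measurement, at the end of three years, loses the subject entirely. By-arm RBANS change is thus reported only for subjects who stayed free of recurrence, and recurrence happens after randomisation.

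Protocol 1.2.5 raises the possibility that treating every episode prevents longer-term morbidity from repeated organ ischaemia. A by-arm table without recurring subjects cannot show a benefit or a harm that operates through recurrence. The total-population summary keeps those subjects but offers no arm comparison.

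A second question follows. The cut-off is worded for endpoints tied to the six-monthly visits, and SAP 2.4.4 does not say whether it reaches event counts. If it does, the number of recurrences by randomised arm can only be 0 or 1 per subject, and TTP-related or thromboembolic events after a first recurrence are left out by arm.

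**Working it through.** The plan gives no sample size, power or expected recurrence rate for C302, so there is no stated figure to reproduce. The check applies the cut-off to the visit schedule and then traces where events are counted.

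**1. RBANS within the by-arm window**
- Scheduled assessments: baseline, and 36 months or early termination.
- For a subject who recurs in C302, both a 36-month visit and an early termination visit after the recurrence fall outside the window.
- Subjects with a post-baseline RBANS and a C302 recurrence in the by-arm table: 0, at any recurrence rate. Baseline RBANS by arm still includes them.

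**2. How many subjects this could be (illustration)**
- Assumptions: 46 per arm (the approximately 92 planned for C301 in protocol 1.2.4, randomised 1:1), everyone rolls over, no exclusions for earlier recurrence, no dropout, RBANS available everywhere. Retained = 46 × (1 − r).
- r = 18%, the literature median in protocol 1.1: 46 × 0.82 = 37.7 retained, 8.3 lost.
- r = 33.3% and 36.1%, exacerbation and/or relapse on placebo and caplacizumab in the Phase II study (protocol 1.2.4): 30.7 and 29.4 retained, 15.3 and 16.6 lost.
- r = 3% and 84%, the literature extremes in protocol 1.1: 44.6 and 7.4 retained.
- Assumed constant annual rate of 8 to 15%: 1 − exp(−3 × 0.08) = 21% and 1 − exp(−3 × 0.15) = 36% over three years.

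**3. Effect on the arm difference (illustration)**
- Assume that subjects without recurrence change equally in both arms and that a recurrence lowers RBANS by d points. Full-follow-up difference = d × (rate in one arm − rate in the other). Truncated difference = 0.
- d = 5 to 15 and rates of 30% and 10%: 5 × 0.20 = 1.0 to 15 × 0.20 = 3.0 points. RBANS is standardised to an SD of 15, so this is 0.07 to 0.20 SD.
- Equal rates: 0 with or without truncation.
- Phase II rates of 36.1% and 33.3%: 5 × 0.028 = 0.14 to 15 × 0.028 = 0.42 points.

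**4. Where events are counted**
- Deaths: SAP 2.4.5.1 tabulates fatal AEs for the ITO population over the overall study period, and SAP 2.4.5.2 lists them. There is no stop at recurrence.
- Recurrences: every exacerbation or relapse is an SAE (protocol 3.5.2), so repeats enter the SAE event counts over the same period. SAP 2.4.4.3 counts recurrences for the ITO population, and the recurrence-population tables describe each episode.
- Grouping: the ITO safety tables split by whether caplacizumab was received in C301, open-label use included (SAP 2.4.5). Placebo subjects who crossed over are therefore in the caplacizumab group. No whole-study count by randomised arm is specified.
- Time to first recurrence and time to first TTP-related event are unaffected, because the first recurrence is itself the event.

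**The case against.** The strongest defence is that the truncation is deliberate. After a recurrence, eligible subjects in both arms receive open-label caplacizumab, so later data no longer contrast caplacizumab with standard of care. The rule was already in the protocol, every analysis is descriptive, and the only RBANS comparison named is with the reference population. Benefit from the C301 index episode also remains visible in subjects who never recur. All of this stands. It justifies keeping the truncated table, but not making it the only by-arm one.

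A reader might infer that mortality omits deaths after a recurrence. The documents do not support this: fatal AEs are counted for the whole study by C301 exposure group. Those groups differ from the randomised arms chiefly through placebo subjects who crossed over in C301 after a recurrence, whom the group-wise analyses exclude anyway.

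A reader might also take the rule that "Q6M visits that are scheduled within a recurrence period will not be held" as a further loss of 36-month RBANS in the by-arm table. It is not additional, since such subjects have already recurred. The ±1 month window also rescues most visits. Taking the Phase II mean of 5.9 daily exchange days on caplacizumab, one recurrence period lasts about 5.9 + 30 + 7 = 43 days, or 71 with the full 28-day extension. Against a window of about 61 days, only the longer period can block the visit, for about 10 days of start dates. At 8 to 15% per year that is 0.08 × 10/365 = 0.2% to 0.15 × 10/365 = 0.4%.

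**Conclusion.** The point holds for RBANS and needs no assumed rate: by-arm post-baseline and change scores contain no subject who recurred in C302. That conditions a listed main endpoint on a post-randomisation outcome.

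The size is uncertain. The 21 to 36% rests on a constant annual rate that the documents do not give, and protocol 1.1 suggests that risk is highest in the first year. The Phase II proportions are of similar size but count from the acute episode, so they are only a rough guide. Whether the arm difference is distorted depends on unequal recurrence. In the Phase II study, combined exacerbation and/or relapse was nearly equal, so the distortion may be nil.

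For event counts, the documents support a request for clarification, not a finding of omission. No error rate or power is affected. This is a cheap improvement to a descriptive plan.

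**What to change.** Keep the truncated group-wise analysis and the time-to-first-event analyses. In SAP 2.4.4:

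- Add descriptive summaries by C301 randomised arm over full follow-up, without truncation, for RBANS (36-month or early termination value and change), SF-36, number of recurrences, TTP-related events and deaths.
- Label these tables as by original randomisation regardless of later treatment. State whether their denominators include subjects left out of the group-wise analyses for an earlier recurrence.
- State whether the first-recurrence cut-off applies to event counts or only to assessments made at the six-monthly visits.

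Splitting by recurrence status should not be the main presentation, because it conditions on the same post-randomisation outcome. The cost is a few descriptive tables from data already scheduled, with no change to visits and no multiplicity consequence. The downside is that post-recurrence data include open-label caplacizumab in both arms, which the label makes plain.

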The efficacy and safety of caplacizumab in the treatment of acquired TTP have been evaluated in Study ALX-0681-2.1/10 comparing it to placebo when added to daily PE and in the 30-day post-daily PE period [16]. The study was terminated early due to recruitment challenges, with a total of 75 subjects enrolled and included in the intention-to-treat (ITT) analysis. The primary endpoint was the time to confirmed normalization of the platelet count. The median time to confirmed response was 2.97 days in the caplacizumab treatment group and 4.79 days in the placebo group. Based on the stratified log-rank test, the time to response was significantly shorter in the caplacizumab treatment group, compared with the placebo treatment group ($p=0.005$), taking into account presence or absence of one PE session prior to randomization. This is also demonstrated by a hazard (i.e., event rate) ratio (95% confidence interval) for the caplacizumab versus placebo treatment groups of 2.197 (1.278, 3.778).

The secondary endpoints illustrate the potential protective effect of caplacizumab treatment in the acute phase of TTP.

- A substantially higher number and proportion of subjects in the caplacizumab treatment group achieved complete remission following the initial course of daily PE compared with subjects in the placebo treatment group (29 [80.6%] subjects versus 18 [46.2%] subjects, respectively).
- Fewer subjects in the caplacizumab treatment group had exacerbations of TTP compared with the placebo treatment group (3 [8.4%] and 11 [28.2%] subjects, respectively).
- A similar number and proportion of subjects in the caplacizumab treatment group and the placebo treatment group had an exacerbation and/or a relapse of TTP (13 [36.1%] and 13 [33.3%] subjects, respectively). This suggests that in a number of subjects, the underlying auto-immune activity had not sufficiently resolved. Immunosuppressive treatment was not standardized and the shorter duration of PE in the caplacizumab arm may also have impacted the timing of the resolution of the underlying auto-immune disorder.
- The mean number of PE days during the initial daily PE period was lower in the caplacizumab group compared with the placebo group (5.9 versus 7.9, respectively), as was the mean total volume of PE administered (19923 mL versus 28307 mL, respectively).

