2.1.3.5.5 Time to first recurrence of aTTP

The event of interest is the first recurrence of aTTP experienced by the patients in the ALX681-C302 study. Time to first recurrence (in days) is defined as the date from end of previous aTTP episode in the ALX0681-C301 study to the date of the event. Patients without an aTTP recurrence during the ALX0681-C302 study are censored at the end of the study. This endpoint is only computed for subjects who did not have any recurrence in the ALX0681-C301, or between the end of ALX0681-C301 trial and the beginning of the ALX-0681C302 trial.

2.1.3.5.6 Time to major thromboembolic events:

The time to the first major thromboembolic event (in days) is defined as the date from screening/baseline visit to the date of the first thromboembolic event. Patient without a thromboembolic event are censored at the end of the study.

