2.4.4.9 Additional efficacy analysis

2.4.4.9.1 Subgroup Analysis

The following endpoints will be summarized for participants with ADAMTS13 activity at the end of the previous TTP (end of the treatment period of the last recurrence episode in the ALX0681C301 trial) $< 10\%$ / $\geq 10\%$ on the ITO population. Subgroup analysis will only be conducted for each subgroup category if at least 5 participants are available.

- Incidence of recurrence of aTTP

Furthermore, the same analysis will be performed by number of recurrences in the ALX0681-C301 trial (1 recurrence, more than 1 recurrence).

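### The arm-wise efficacy comparison excludes subjects who recurred before C302 baseline, and no efficacy summary of all ITO subjects by C301 randomised arm is planned beside it

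*SAP*

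**What the plan says.** SAP 2.4.4 defines two groups for the Q6M efficacy endpoints. The comparator is the ITO subjects "randomized to placebo in study ALX0681-C301, evaluated up to their first recurrence in the ALX0681-C302 trial", and the caplacizumab group is defined in the same way. The section then removes some of them: "Subjects who had a recurrence during study ALX0681-C301 or between the Final (28 day) FU visit" and the C302 baseline "will not be considered for the group-wise analyses". The footnote to Protocol 3.6.4 carries the same rule, so it was pre-specified.

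Other planned summaries touch on the point:

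- **Total population (SAP 2.4.4).** "Summarization will be conducted on the total study population and by analysis group". The total-population part is a single group with no arm split.
- **Time to first recurrence (SAP 2.1.3.5.5).** "This endpoint is only computed for subjects who did not have any recurrence in the ALX0681-C301" study, or in the gap before C302. The exclusion is part of the endpoint definition, so it also restricts the total-population curve.
- **Subgroups (SAP 2.4.4.9.1).** For incidence of recurrence, "the same analysis will be performed by number of recurrences in the ALX0681-C301 trial" (one, or more than one). No split by arm is stated.
- **Safety (SAP 2.4.5).** All ITO subjects are kept, but grouped by whether they received caplacizumab in C301. A placebo subject who crossed over counts as caplacizumab.
- **Sensitivity (SAP 2.4.4).** "Select sensitivity analyses may be planned to assess the effect of heterogeneity in the timings of the baseline visit between subjects". This is optional and does not concern the exclusion.

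**The concern.** The group labels point to randomised arms, but membership depends on what happened after randomisation. Recurrence over the whole of C301 is that trial's second key secondary endpoint (Protocol 1.2.4), and Protocol 1.2.5 names fewer exacerbations on treatment as a possible benefit. If treatment changes who recurs early, and early recurrence marks patients likely to recur again, the remaining groups differ in underlying risk even with no long-term treatment effect.

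The documents give reason to think early recurrence is prognostic. Protocol 1.1.1 describes severe ADAMTS13 deficiency as a potential marker of relapse risk. In the phase II TTP trial (Protocol 1.2.4), activity was below 10% in 7 of 9 placebo subjects with an exacerbation and available data, and in 7 of 8 caplacizumab subjects who relapsed in the first month.

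A second consequence holds whichever way the selection runs. Protocol 1.1 and 1.2.5 argue that repeated episodes may cause cumulative damage which treatment might avert. Dropping subjects with an early recurrence removes that pathway from the arm comparison of TTP-related events, cognition and quality of life. Long-term efficacy is part of the first study objective.

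**Working it through.** The plan gives no sample size, power or expected event count for C302, and no C301 results, so there is no design figure to reproduce. What follows is illustration.

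**Inputs from Protocol 1.2.4**

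- C301 planned about 92 subjects, 1:1, so 46 per arm.
- Phase II exacerbations, caplacizumab and placebo: "3 [8.4%] and 11 [28.2%] subjects, respectively". Denominators are 36 and 39; 3/36 = 8.3% (printed as 8.4%) and 11/39 = 28.2%.
- Phase II exacerbation and/or relapse: 13/36 = 36.1% and 13/39 = 33.3%. Relapse without exacerbation therefore accounts for 13 - 3 = 10 and 13 - 11 = 2 subjects.
- Seven caplacizumab subjects relapsed 4 to 10 days after stopping drug, which would fall inside C301's 28-day follow-up.

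**Subjects excluded, if all 46 per arm enrolled**

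- Exacerbation rates: 46 × 3/36 = 3.8 and 46 × 11/39 = 13.0.
- Total recurrence rates: 46 × 13/36 = 16.6 and 46 × 13/39 = 15.3.

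**Model A: every early recurrer is high-risk.** Assume a high-risk share h = 0.35, with 36-month recurrence of 50% (high risk) and 15% (low risk) in both arms. Without exclusion, both arms show 0.35 × 50% + 0.65 × 15% = 27.3%. With early-recurrence rate r, the high-risk share among those kept is s = (h - r)/(1 - r), and their recurrence is 50% × s + 15% × (1 - s).

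| Early recurrence, caplacizumab vs placebo | s | Recurrence among those kept | Difference (points) |
|---|---|---|---|
| 3/36 vs 11/39 (exacerbations only) | 29.1% vs 9.5% | 25.2% vs 18.3% | +6.9 |
| 10/36 vs 11/39 (7 early relapses added) | 10.0% vs 9.5% | 18.5% vs 18.3% | +0.2 |
| 10/36 vs 13/39 (all placebo relapses also added) | 10.0% vs 2.5% | 18.5% vs 15.9% | +2.6 |
| 13/36 vs 13/39 (all recurrences) | (0.35 - 0.361)/0.639 is negative | not defined | not defined |

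The 10/36 assumes no overlap between the three exacerbators and the seven early relapsers. The two placebo rates cover the unknown timing of the placebo relapses.

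**Model B: early recurrence is only partly predictive.** Assume h = 0.3 or 0.5 and long-term recurrence of 50% (high risk) and 10% (low risk). The early-recurrence risk ratio, high to low, is k = 1, 2, 4 or 8. Then r_L = r/(hk + 1 - h), r_H = k × r_L, and s = h(1 - r_H)/[h(1 - r_H) + (1 - h)(1 - r_L)].

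Worked case, h = 0.3, k = 8, exacerbation rates:

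- Caplacizumab: r_L = 0.0833/3.1 = 0.027, r_H = 0.215, s = 0.257, recurrence 20.3%.
- Placebo: r_L = 0.282/3.1 = 0.091, r_H = 0.728, s = 0.114, recurrence 14.5%.
- Difference: +5.7 points from unrounded values.

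| Rates used | h | k = 1 | k = 2 | k = 4 | k = 8 |
|---|---|---|---|---|---|
| Exacerbations only | 0.3 | 0.0 | +2.0 | +4.0 | +5.7 |
| Exacerbations only | 0.5 | 0.0 | +2.0 | +3.6 | +4.7 |
| All recurrences | 0.3 | 0.0 | -0.4 | -0.9 | -1.2 |
| All recurrences | 0.5 | 0.0 | -0.4 | -0.8 | -1.0 |

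Across both models the spurious difference runs from about -1 to +7 points. It vanishes in Model B only when early recurrence carries no information about later recurrence (k = 1).

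**The case against.** The strongest reply has four parts.

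**The exclusion has a plausible purpose.** In C301, a first exacerbation, or a first relapse during treatment extension, leads to open-label caplacizumab (Protocol 1.2.4). Keeping such placebo subjects in a group named standard of care-treated would mix exposures. The documents state no reason, so this is inference, but it is sensible. It justifies keeping the planned analysis. It does not remove the selection, and neither does pre-specification.

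**Nothing is tested.** SAP 2.4.4.8 confirms that no formal test is planned, so no type I error is at stake. Arm-wise percentages and Kaplan-Meier curves will still be read as evidence on long-term efficacy.

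**The imbalance may be small.** The rule removes relapses as well as exacerbations, and phase II totals were similar (36.1% versus 33.3%). The subjects removed may also be alike on the one marker reported: all seven early caplacizumab relapsers, and 7 of 9 placebo exacerbators with data, had ADAMTS13 activity below 10%. This stands as a reason not to assert a direction. One might reply that C301's treatment extension will prevent the relapses, but Protocol 1.2.5 presents that as a question to be evaluated. Similar totals do not establish comparability either, because the mix of event types differed (10 versus 2 subjects counted through relapse alone).

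**An all-ITO comparison is selected too.** C302 takes only C301 completers who choose to join. That is true, and is a limit to state beside the added tables.

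**Conclusion.** The point holds as an openness to selection bias of unknown size and direction. The planned arm comparison conditions on a post-randomisation outcome that treatment may affect, and no efficacy summary by C301 randomised arm shows what happens without that condition.

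Two stronger readings are tempting, and the documents support neither.

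- A reader might infer that the comparison is biased against caplacizumab by about 7 points. That figure needs exacerbation-only rates and every early recurrer to be high-risk. Adding the seven early relapses cuts it to between 0.2 and 2.6 points in the same model, and total recurrence rates reverse the sign in Model B. No C301 recurrence counts by arm are given.
- A reader might infer that no unselected analysis is planned at all. Total-population efficacy summaries and ITO safety tables are planned. The gap is specific to efficacy by randomised arm, plus the total-population time to first recurrence.

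The range of -1 to +7 points rests on assumed risk classes and phase II rates and is not a bound. In the first Model A scenario, a high-risk recurrence rate of 40% or 60% would give (0.291 - 0.095) × 25 = 4.9 or (0.291 - 0.095) × 45 = 8.8 points. The exclusion counts also assume that all 46 per arm enrol. The change is worth making because it is cheap and lets readers see the effect of the selection.

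**What to change.** 1. Keep the planned group-wise analysis, and label its tables and figures as conditional on no recurrence before C302 baseline.
2. Report the number excluded per C301 randomised arm, separating recurrences in C301 from those in the gap before C302 baseline.
3. Add supplementary descriptive event summaries and Kaplan-Meier curves for all ITO subjects by C301 randomised arm, showing how many in each arm had crossed over to open-label caplacizumab.
4. In that supplement, start time to first recurrence at C302 screening/baseline for everyone. The current origin, the end of the previous C301 episode, gives no common starting point once subjects with earlier recurrences are included.

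The cost is a few extra tables and figures, with no new data collection. The downside is interpretive. The added comparison mixes in placebo subjects who crossed over and covers only C301 completers who enrolled, so it should be presented as a treatment-policy companion to the planned analysis and not as its replacement.
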